13.1.1 Adverse Events of Special Interest

An AESI is a noteworthy treatment-emergent event for the study drug that should be monitored closely and reported promptly. See Section 13.1.4 for reporting procedure. An AESI can be either serious or non-serious.

Based on the potential risks of nemolizumab and the risks associated with biologics (and their biosimilar equivalents) in general (ie, class effects), the following AEs will be considered AESIs:

- Injection-related reactions
 - Anaphylactic reactions
 - Acute allergic reactions requiring treatment
 - Severe injection site reaction (ie, lasting > 24 hours)
- Newly diagnosed asthma or worsening of asthma
 - More specifically, subjects with a medical history of asthma will be referred to the physician who manages their asthma when:
 - ACT score \leq 19: An ACT score \leq 19 conveys asthma that may not be adequately controlled. An AESI is reported based on the investigator's clinical judgment, including consideration of the managing physician's report.
 - PEF $<$ 80% of the predicted value: An AESI should be reported.
 - Unexpected worsening of asthma is observed or reported. An AESI is reported based on the investigator's clinical judgment.
 - Subjects without a medical history of asthma will be referred to an appropriate respiratory physician/specialist when:
 - Signs and/or symptoms suggestive of asthma have been observed or reported. An AESI is reported based on the investigator's clinical judgment of the specialist's report.

This document is confidential.

Page 82 of 133

- Respiratory assessments (eg, examination, PEF) suggest a decline in the subject's respiratory health. An AESI is reported based on the investigator's clinical judgment of the specialist's report.
- Infections
 - Any severe infection or any infection requiring treatment with parenteral antibiotics or oral antibiotics/antivirals/antifungals for > 2 weeks
 - Any confirmed or suspected COVID-19 infection
- Peripheral edema: limbs, bilateral
- Facial edema
- Elevated ALT or AST ($> 3 \times$ ULN) in combination with elevated bilirubin ($> 2 \times$ ULN)

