6.1.2 Secondary Objectives

The secondary objectives are to assess the safety and efficacy of nemolizumab (CD14152) after a 16-week treatment period in adult and adolescent subjects with moderate-to-severe AD.

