7 INVESTIGATIONAL PLAN

7.1 Description of Overall Study Design and Plan

This is a randomized, double-blind, placebo-controlled, multi-center, parallel-group study in adult and adolescent subjects (≥ 12 to 54 years) with moderate-to-severe AD. Eligible subjects must have a documented history of inadequate response to topical AD medication(s).

Approximately 245 subjects will be randomized 1:1 to receive either 30 mg nemolizumab (with a 60 mg loading dose) or placebo, stratified by baseline disease severity **CCI** **16.9**.

The study consists of 3 periods with up to 28 weeks total study duration: a 2- to 4-week screening period, a 16-week treatment period, and an 8-week follow-up period (12 weeks after the last study drug injection).

Screening Period

The screening period will evaluate subject eligibility. Subjects will apply a moisturizer at least once daily, beginning at screening. Subjects using a stable regimen of low- or medium-potency TCS with or without topical calcineurin inhibitor (TCI) at the screening visit (ie, ≥ 14 days prior to the baseline visit) should continue their therapy regimen. Subjects not using a stable regimen of TCS with or without TCI at the screening visit should not use these topical therapies during the study unless required as rescue therapy.

Rescue therapies are not permitted during the screening period.

Treatment Period

At the baseline visit, subjects will receive a loading dose of nemolizumab (60 mg) or placebo via 2 subcutaneous injections. Nemolizumab (30 mg) or placebo will then be administered via a single subcutaneous injection Q4W at Week 4, 8, and 12. At the Week 12 visit, subjects will also receive single doses of **PPD** **vaccines**. Clinical assessments will occur according to the schedule of assessments in **Table 4**.

This document is confidential.

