9 TREATMENTS

9.1 Details of Study Drug and Vaccines

9.1.1 Study Drug

“Study drug” or “study medication” refers to nemolizumab or placebo drug product for purposes of this double-blind study. The list of excipients are detailed in the IB.

Nemolizumab 30 mg and placebo will be provided as lyophilized powder for solution for injection for subcutaneous use only after reconstitution in a pre-filled, single-use, dual-chamber syringe (DCS).

The lyophilized nemolizumab (CD14152) powder (39 mg) and solution for reconstitution (0.595 mL) are stored in separate syringe chambers, with each DCS designed to deliver a 30-mg dose of nemolizumab (CD14152) after reconstitution.

Subjects will receive a loading dose of nemolizumab (eg, 60 mg) or placebo by 2 SC injections at baseline and a single 30-mg dose at Weeks 4, 8, and 12.

CCI

This document is confidential.

Page 55 of 133

CCI

[figure not shown]

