9.2 Dosage Schedule

[Table 2](#) summarizes study drug dosing for the 16 week treatment period.

Table 2: Treatment Period Dosing By Treatment Group

Treatment Group	Dose/route	Week(s)	Schedule
Nemolizumab (CD14152)	30 mg × 2 SC injections	Baseline	Baseline
	30 mg × 1 SC injections	4, 8, 12	Q4W
Placebo	Placebo× 2 SC injections	Baseline	Baseline
	Placebo× 1 SC injections	4, 8, 12	Q4W

Abbreviation(s): Q4W=every 4 weeks; Q8W=every 8 weeks; SC=subcutaneous.

Tdap and MCV4 will be administered separately each as a 0.5 mL intramuscular injection at Week 12.

Subjects requiring any rescue therapy during the screening period are ineligible for participation in the study. Subjects requiring systemic rescue therapy during the treatment period prior to Week 16 must discontinue study treatment.

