9.7.1 Early Termination Visit

Subjects may discontinue from the study or discontinue the study treatment only and continue to participate in the study.

Subjects who prematurely discontinue from the study should undergo final study assessments according to the following guidelines:

- Subjects discontinued from the study during the treatment period on/before the Week 16 visit should attend an early termination visit.
- A follow-up/final visit is required 12 weeks after the last study drug administration.

Subjects who prematurely discontinue the study drug will be asked to continue participation in the study; however, subjects who discontinue the study drug prior to Week 12 should not be vaccinated. Subjects will be asked to return for all remaining visits and assessments (including daily assessment of pruritus, sleep disturbance, etc). Participation will continue until the subject completes the final study visit or otherwise discontinues study participation.

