Adverse events assessed as related to the treatment or study procedure will be monitored until they have resolved or reached a stable condition. Other AEs will be monitored until the last visit if they have not resolved or reached a stable condition.

The investigator will obtain and maintain in the subject’s files all pertinent medical records, information and medical judgment from colleagues who assisted in the treatment and follow-up of the subject. If necessary, the investigator will contact the subject’s personal physician or hospital staff to obtain further details.

Assessment of Severity

Each AE will be assigned a category by the investigator as follows:

Mild: An AE that is easily tolerated by the subject, causes minimal discomfort, and does not interfere with everyday activities.

Moderate: An AE that is sufficiently discomforting to interfere with normal everyday activities; intervention may be needed.

Severe: An AE that prevents normal everyday activities; treatment or other intervention usually needed.

If there is a change in severity of an AE, it must be recorded as a separate event.

Assessment of Causality

The investigator is to determine whether there is a reasonable causal relationship between the occurrence of the AE, and exposure to the study drug (ie, nemolizumab or placebo) and/or study procedure (eg, injection, topical background therapy, blood sample collection). Medical judgment should be used to determine the relationship, considering all relevant factors including the pattern of the reaction, temporal relationships, relevant medical history, and confounding factors such as co-medication or concurrent diseases.

The expression “reasonable causal relationship” is meant to convey in general that there are facts or arguments to suggest a causal relationship (International Council for Harmonisation [ICH] E2A, Section IIIA 1).

The relationship assessment for an AE is to be completed using the following definitions as a guideline for all AEs occurring during this clinical study:

Reasonable possibility:

According to the reporting investigator, there is a reasonable possibility (ie, suggestive evidence or arguments) that there is a causal relationship irrespective of the dose administered:

- Between the study drug (nemolizumab) and the AE, and/or
- Between the clinical study protocol procedure (eg, injection, topical background therapy, blood sample collection) and the AE

No Reasonable Possibility:

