## 10.3. Adverse Events / Adverse Drug Reactions

Adverse events (AEs) will be coded using MedDRA Version 25.0.

Treatment-emergent AEs (TEAEs) is defined as AEs with an onset date on or after the first dose date of study treatment. Partially missing date will be handled using the algorithm described in Section 6.3. AE

related to study drug is defined as AE with a relationship to study drug reported as 'Reasonable Possibility' or missing.

Summary table for adverse events will include the number and percent of subjects and the numbers of events by treatment group and by System Organ Class (SOC) and Preferred Term (PT). SOC and PT within each SOC will be sorted by descending overall frequency. Subjects who have multiple events in the same SOC and the same PT within each SOC will be counted only once in the subject counts, but all events will be considered and presented (if applicable). For summary by maximum severity, subjects who experience multiple occurrences of an AE, the most severe category for each SOC and for each PT within each SOC will be considered in the summary.

The summary tables for following TEAEs will be presented:

- Overall Summary: summary of the number and percentage of subjects reporting TEAEs, TEAEs by
  maximum severity, serious TEAEs, study drug-related TEAEs, drug-related serious TEAE, study
  drug-related TEAEs by maximum severity, treatment-emergent AESI, Confirmed or suspected
  COVID-19 infection, TEAEs leading to study drug withdrawal, TEAEs leading to study drug
  interruption, TEAEs leading to study discontinuation, and TEAEs leading to death
- The total number and incidence of TEAEs by SOC and PT
- The total number and incidence of Serious TEAEs by SOC and PT
- The total number and incidence of TEAEs related to study drug by SOC and PT
- The total number and incidence of serious TEAEs related to study drug by SOC and PT
- The total number and incidence of TEAEs by SOC, PT, and maximum severity
- The total number and incidence of drug-related TEAEs by SOC, PT, and maximum severity
- The total number and incidence of TEAEs leading to temporary interruption of study drug by SOC and PT
- The total number and incidence of TEAEs leading to permanent discontinuation of study drug by SOC and PT
- The total number and incidence of TEAEs leading to study discontinuation by SOC and PT
- The total number and incidence of TEAEs of special interest by SOC and PT

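### Reactions to the two Week 12 vaccines are pooled into the TEAE counts and, through ambiguous wording, can enter the injection-reaction AESI and drug-related counts, with no planned table to separate them

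*Protocol*

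**What the plan says.** Protocol 6.1.2 sets the safety question: "The secondary objectives are to assess the safety and efficacy of nemolizumab (CD14152) after a 16-week treatment period". Protocol 9.1.1 defines study drug as nemolizumab or placebo, so the vaccines are not study drug. It schedules "a single 30-mg dose at Weeks 4, 8, and 12" after the loading dose. Protocol 9.2 adds, for both arms, "Tdap and MCV4 will be administered separately each as a 0.5 mL intramuscular injection at Week 12". A subject who follows the schedule therefore has three injections at that visit.

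SAP 10.3 states: "Treatment-emergent AEs (TEAEs) is defined as AEs with an onset date on or after the first dose date of study treatment". Protocol 16.6 closes the window 84 days after the last dose or at rollover to the extension study. Either way, the time after vaccination is covered.

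Protocol 13.1.1 describes an AESI as an event of note for the study drug, but the injection item reads "Severe injection site reaction (ie, lasting > 24 hours" and does not say which injection. Protocol 13.1.4 requires AESIs to be reported whether or not they are judged related.

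Under Assessment of Causality in Protocol 13.1, a reasonable possibility can rest on the study drug and/or a "study procedure (eg, injection, topical background therapy, blood sample collection"). Vaccination is not a category. SAP 10.3 counts an event as drug-related if its relationship to study drug is a reasonable possibility or is missing.

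Vaccination is conditional. Protocol 9.7.1 says that "subjects who discontinue the study drug prior to Week 12 should not be vaccinated", and Protocol 16.4.1 and SAP 8.1.1 say that subjects on systemic rescue are not vaccinated.

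**The concern.** Local and systemic injection-related reactions head the list of important potential risks of nemolizumab in Protocol 5.3.1. The planned AE outputs are counts and percentages by arm, so readers will judge this risk from those percentages. If reactions to Tdap and MCV4 are in the same rows, each arm's figure mixes two sources and a modest effect of the drug injection is harder to see. Because vaccination depends on staying on drug and off systemic rescue, the vaccinated share could also differ by arm, while the safety population in SAP 5.2 keeps everyone dosed in the denominator.

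**Working it through.** The plan gives no figure to reproduce here. The check has a textual part and an arithmetic part, and all reaction rates below are assumptions.

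**Text**

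| Count | Do vaccine reactions enter? | Basis |
|---|---|---|
| TEAEs | Yes | SAP 10.3 and Protocol 16.6 define them by onset date only |
| Injection-reaction AESI | Possibly | Protocol 13.1.1: injection not named, although AESIs are events for the study drug |
| Drug-related TEAEs | Possibly | Protocol 13.1: a procedure such as an injection can satisfy the category; SAP 10.3 also counts missing relationship |

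The visible SAP 10.3 text and the table index (SAP 17) contain no split before and after vaccination, no vaccine-related AE table and no AESI table by injection.

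The AESI item explains severe by duration (over 24 hours). Assessment of Severity in Protocol 13.1 defines it by whether normal activities are prevented. On its wording, a mild local reaction lasting over a day could qualify as the AESI.

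**Dilution**

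Let d be the risk of a study-drug reaction, v the risk of a qualifying vaccine reaction if vaccinated, and s the vaccinated share. With independence, the pooled risk is p = 1 − (1 − d)(1 − v·s).

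Example A: d = 3% on nemolizumab and 1% on placebo, s = 1. Ratio = (0.03 + 0.97v)/(0.01 + 0.99v); difference = 0.02(1 − v).

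| v | Nemolizumab | Placebo | Ratio | Difference (points) |
|---|---|---|---|---|
| 0 | 3.0% | 1.0% | 3.0 | 2.0 |
| 10% | 12.7% | 10.9% | 1.17 | 1.8 |
| 20% | 22.4% | 20.8% | 1.08 | 1.6 |
| 30% | 32.1% | 30.7% | 1.05 | 1.4 |

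Example B: d = 10% and 2%, s = 1, 123 per arm. Power is for a two-sided 5% comparison, Φ[(Δ − 1.96·SE₀)/SE₁], with SE₀ pooled and SE₁ unpooled. The SAP plans no such test; power here only measures how visible the signal is.

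| v | Ratio | Difference (points) | Power |
|---|---|---|---|
| 0 | 5.00 | 8.0 | 75.5% |
| 5% | 2.10 | 7.6 | 48.7% |
| 10% | 1.61 | 7.2 | 34.5% |
| 20% | 1.30 | 6.4 | 21.2% |
| 40% | 1.12 | 4.8 | 11.5% |

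**Spurious difference**

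With no drug effect (d the same in both arms), the expected difference is (1 − d)·v·(s₁ − s₀), which is exactly 0 when s₁ = s₀. With d = 2%:

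| v | 95% vs 85% vaccinated | 95% vs 80% vaccinated |
|---|---|---|
| 5% | 0.5 points | 0.7 points |
| 10% | 1.0 | 1.5 |
| 20% | 2.0 | 2.9 |
| 30% | 2.9 | 4.4 |
| 40% | 3.9 | 5.9 |

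For scale, at 95% vs 85% and v = 20%, p is 20.6% vs 18.7%. The standard error of the difference at 123 per arm is √[(0.206·0.794 + 0.187·0.813)/123] ≈ 5.1 points. At v = 30% it is about 5.8.

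**The case against.** A reader might infer that vaccine reactions can pass for a nemolizumab effect in general. They cannot. Both arms are vaccinated at the same visit, so with equal shares and no interaction the expected difference is zero. If nemolizumab did change vaccine reactions, that would be an effect of nemolizumab. Unequal shares are possible: treatment failure and systemic rescue are listed reasons for stopping drug (Protocol 8.4), and the 30-mg dose beat placebo in Phase 2b (Protocol 5.2.3.1). But the documents give neither the shares nor their direction, and the illustrated 2 to 3 points are smaller than one standard error.

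A reader might also infer that the AESI expressly counts vaccine-site reactions. Section 13.1.1 ties AESIs to the study drug, so a narrower reading is natural. The rule on reporting regardless of relatedness does not decide which injection qualifies. The defect is ambiguity.

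The fall in the ratio overstates the loss, since the risk difference moves much less and the SAP plans no AE ratio. Investigators must weigh timing and co-medication when judging causality, and whether the eCRF separates drug from procedure cannot be seen. Tables are by system organ class and preferred term, so asthma, edema and infection keep their own rows. Onset dates, AESI listings, vaccine administration and study-drug injection sites are recorded, so timing can be recovered.

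All of this stands, and it limits the size of the point. It does not remove the gap: listings support case review, but no planned table makes the separation.

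**Conclusion.** The point holds as one of pooling and ambiguous scope. Vaccine reactions enter the TEAE counts and can enter the injection-reaction AESI and drug-related counts. The consequences are inflated incidence in each arm and a weaker contrast for nemolizumab's own injection reactions. Under the assumed rates the ratio shrinks sharply and the absolute difference modestly. Bias between arms arises only if the vaccinated shares differ.

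A reader might go further and want the pre-vaccination period as the main safety estimate. The documents do not support that: it would drop everything after the Week 12 dose, although the objective covers 16 weeks of treatment and the protocol window runs 84 days past the last dose. Confining the whole injection-reaction AESI to study-drug injections is not supported either, because a systemic reaction after same-visit injections cannot be assigned to one of them.

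The sizes rest on assumed rates, assumed shares and independence. The textual finding rests on the visible text only; redacted sections could hold more.

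**What to change.** 1. **SAP 10.3.** Keep the pooled tables over treatment and follow-up as the main safety summary. Add supportive TEAE, drug-related TEAE and AESI tables by arm for (a) onset before vaccination, in the safety population, and (b) onset on or after vaccination, in vaccinated subjects. Show the number vaccinated per arm, which SAP 10.1 already tabulates. Note that (b) selects on a post-randomization event, and state where later events in unvaccinated subjects are counted.
2. **Protocol 13.1.1.** For each injection-site reaction, record whether it is at a study-drug or a vaccine site, and tabulate the two separately. Keep reporting systemic reactions after same-visit injections as AESIs, marked as not attributable to one injection.
3. **Protocol 13.1 and 13.1.1.** Reconcile the two meanings of severe.

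Item 1 uses AE onset dates and vaccine administration data that are already collected. The cost is a few more tables, one attribute per reaction, and smaller counts in each period.

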13.1.2 Serious Adverse Events

An SAE is any untoward medical occurrence or effect that, at any dose,

- Results in death.
- Is life-threatening (an AE is life-threatening if the subject was at immediate risk of death from the event as it occurred, ie, it does not include a reaction that might have caused death if it had occurred in a more serious form).
- Requires or prolongs inpatient hospitalization. (Complications occurring during hospitalization are AEs and SAEs if they cause prolongation of the current hospitalization. Inpatient hospitalization is considered to have occurred if the subject has had to stay for a night at the hospital. The criterion for prolongation of hospitalization is also defined as an extra night at the hospital. Hospitalization may not constitute sufficient grounds to be considered as an SAE if it is solely for the purpose of diagnostic tests [even if related to an AE], elective hospitalization for an intervention that was already planned before subject enrollment in the clinical study, admission to a day care facility, social admission [eg, if the subject has no place to sleep], or administrative admission [eg, for a yearly examination].

This document is confidential.

The details of such hospitalizations must be recorded on the medical history or physical examination eCRF.)

- Results in persistent or significant disability/incapacity. (An AE is incapacitating or disabling if it results in a substantial and/or permanent disruption of the subject's ability to carry out normal life functions.)
- Results in a congenital anomaly/birth defect.
- An important medical event that may not result in death, be life-threatening, or require hospitalization, may be considered an SAE when, based upon appropriate medical judgment, the event may jeopardize the safety of the subject, and may require medical or surgical intervention to prevent 1 of the outcomes listed above in this definition. Examples of such events are intensive treatment in an emergency room or at home for allergic bronchospasm, blood dyscrasias, or convulsions that do not result in hospitalization.

13.1.3 Procedure for Reporting a Serious Adverse Event

For any SAE occurring during the clinical study, regardless of whether or not related to the study drug and/or procedure, the investigator must:

1. Take prompt and appropriate medical action, if necessary. The safety of the subject is the first priority.
2. Ensure that the event is evaluated as an SAE. Immediately notify (**within 24 hours of receipt of the event**) the **PPD** group of an SAE report, by email or fax:

PPD

[REDACTED]

[REDACTED]

Note: Immediate SAE reporting is required by the investigator if it occurs during the clinical study or within 12 weeks (\pm 5 days) of receiving the last dose of study drug, whether or not the event is considered to be related to the investigational product.

This document is confidential.

Page 84 of 133

The demographics, medical history, drugs/therapies, and medical and surgical procedures forms must also be available for review in eCRF, at that time.

3. Send any relevant information or anonymized medical records (eg, laboratory test results) to the PPD (see contact details above), within 24 hours of receipt of this relevant information.
4. Monitor and record the progress of the event until it resolves or reaches a stable condition, with or without sequelae. For all additional follow-up evaluations, complete an updated SAE report **within 24 hours** of receipt of the updated information.
5. Obtain and maintain in the subject files all pertinent medical records, information, and medical judgments from colleagues who participate in the treatment and follow-up of the subject. If necessary, contact the subject's personal physician or hospital staff to obtain further details.
6. When the outcome of the event is known, complete an updated SAE report, if appropriate.
7. Prompt notification of SAEs by the investigator is essential so that legal obligations and ethical responsibilities toward the safety of subjects are met. The sponsor has a legal responsibility to notify both the local regulatory authority and other regulatory agencies about the safety of a product under clinical investigation. The sponsor or its delegate (ie, the CRO) will comply with country-specific regulatory requirements relating to safety reporting to regulatory authorities, IRB/IEC and investigators. Investigator safety reports are prepared for SUSARs according to local regulatory requirements, and are forwarded to investigators as necessary.

An investigator who receives an investigator safety report describing an SAE(s) or other specific safety information (eg, summary or listing of SAEs) from the sponsor or its delegate (ie, the CRO) will file it accordingly (ie, within the Trial Master File [TMF]), and will notify the IRB/IEC, if appropriate according to local requirements.

This document is confidential.

Page 85 of 133

8. Comply with the applicable regulatory requirement(s) related to the reporting of SAEs to the IRB/IEC.

